The use of fitness technology services could have beneficial effects on chronic disease management in late life, including positive changes in health perception, social functioning, and mental health (Lindeman et al., 2020). Fitness technology is regarded as a vital means for maintaining and enhancing older people's quality of life (Khosravi et al., 2016; Mitzner et al., 2018). In addition, previous research also indicated that information communication technologies could provide a link between older adults and their informal and formal networks. Technologies allow older adults to transcend spatial barriers and provide them a greater sense of connection to other people (Clarke et al., 2009; Schlomann et al., 2020). Exploring the role of social factors in increasing physical activity using technology is a promising direction (Zhang et al., 2016).

Objectives

This paper reports on the use of WeChat to improve physical and social activity among community dwelling older adults. WeChat is a free mobile text and voice messaging communication service. This pilot study explored the efficacy of one function of the app WeChat: a group-based pedometer function WeRun. There are previous empirical studies conducted on WeRun with younger adults; for example, Gui and colleagues (2017) conducted a qualitative study of 32 users of WeRun. Their findings indicated that sharing fitness data with pre-existing social networks motivated users to continue self-tracking their steps and enhanced their existing social relationships.

However, we are not aware of any empirical studies conducted using WeRun with older adults.

The objectives of this study are to explore: a) whether the participants in the treatment group would show greater increases and higher maintenance of daily steps as well as greater increases in level of social engagement and exercise self-efficacy in comparison to the participants in the control group who were not given the treatment; and b) whether social engagement would be a significant mediator, that is a mechanism of behavior change.

Design

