Treatment condition: Participants used WeChat for 4 weeks, during which time the steps data were recorded by the WeRun function and downloaded by the research assistants. The participants in the treatment condition could interact with the other group members by sending text messages which were documented by the research assistants. The researchers sent out instructions to check step counts on Monday mornings during the 4-week intervention, for example "Dear all, this is Week 1! please remember to take your phone with you as often as possible during the day and check your step count in WeRun by the end of the day. Please also share your number of steps with your group members. Thank you!" The daily walking steps of the participants in this group were displayed to the group and the participant with the highest daily steps in the group was indicated as the champion each day.

Control condition: Participants only saw their own daily walking steps using WeChat. They did not see other group members' daily steps and did not interact or compare walking steps with other group members. The participants received messages on

Monday mornings during the 4-week intervention to remind them to take their phones as often as possible during the day.

Methods

Participants

Eligibility. Inclusion criteria specified that participants must be 60 or older and fit enough to walk for at least 20 minutes at a time. They also needed to have a smartphone, with either an Android or iPhone system with Internet access. A power analysis (using G*Power 3.1) for the study and analysis design indicated that a total of 56 participants (randomly assigned across two groups) would provide adequate power ($> 80\%$) to detect medium-sized effects ($\rho = 0.3$) at $p < .05$. We recruited 60 participants in the northeast U.S. by posting recruiting posters in community public posting boards, including public libraries, grocery stores and shopping malls. Participants were given two 25-dollar gift cards (one at the pretest and one after the 4-week intervention) as compensation for their participation.

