Sample. As shown in the consort diagram in Figure S1, of the 241 adults who filled out our eligibility questionnaire online, 38 were not eligible, 15 gave up as they had trouble downloading the app, 4 did not meet the age requirement, 4 indicating participating in a walking intervention would be a potential health risk, and 3 could not participate due to travel. One hundred and forty-three potential participants who were eligible did not respond when we notified them that they were eligible. Recruitment took place from October 2018 to March 2019, with primary data collection completed in February 2019, and follow-up data collection completed in March 2019. Those who were

physically active (i.e., who had 7,000 - 10,000 daily steps or above everyday) were not included after the one-week baseline. A total of 60 adults were recruited and randomly assigned to either the control condition ($n = 30$) or the treatment condition ($n = 30$). They completed the study in one of three subgroups, with 20 participants randomly assigned into two groups (10 in treatment group, and 10 in control group) for each subgroup.

Measures

Covariates. Age, gender, education, race, and self-reported health were used as covariates in the analyses because of their expected relationship with the outcome measures. For physical health, the participants were asked “in general would you say your health is?” The response options ranged from 1 (poor) to 5 (excellent) with a higher score indicating better physical health.

The outcome measures were administered at the pretest, posttest and follow up using self-report questionnaires given before and at the completion of week 4 of the pilot study and at the 1 month follow up through an online platforms-Qualtrics.

Daily step counts. Participants' daily steps were recorded by using the WeRun function in WeChat by the end of each day during the 4-week intervention period and at the 1 month follow up. Mean daily steps for pretest week, post-test week and one month follow up week were calculated as the mean number of steps across the 7 days in that week of the study.

Percentage change in mean weekly steps at posttest was calculated as the difference between the mean weekly steps at posttest and pretest divided by the mean weekly steps at pretest. The percentage change in mean weekly steps at the one month

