Statistical analyses of survey measures were done using SPSS. Descriptive information and correlations were computed for all study variables. Changes in daily steps, social engagement and exercise self-efficacy from the pretest to 4 weeks were examined. Repeated measures ANCOVA was used to test for effects of the treatment on mean daily step counts over the intervention period, exercise self-efficacy, and social engagement and to compare treatment and control groups at pretest, posttest, and follow-up using a two condition by three occasions design. All post hoc analyses were performed using Bonferroni corrections controlling the covariates. We conducted a sensitivity analysis without the covariates and the results were the same.

Conditional process modeling was applied using PROCESS in SPSS to test the predicted mediation model. Mediation analyses was based on 1000 bootstrapped samples using Hayes’ PROCESS Macro v3.3 (Hayes & Preacher, 2014), allowing for formal tests of the total, direct, and indirect effects of intervention on percentage of change of mean weekly steps from pre-test to post test. The predictor variable was condition, the mediator variable was change in social engagement, and the outcome was percent change in mean weekly steps from pre-test to post test.

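### Subgroup, the factor within which people were randomised 10:10, is missing from both models; adding it costs almost nothing but must come with a statement of whether inference goes beyond the three groups run

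*Combined protocol and SAP*

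**What the plan says.** Under Sample, the protocol describes three subgroups of 20, "with 20 participants randomly assigned into two groups (10 in treatment group, and 10 in control group) for each subgroup". That gives 30 per arm, balanced within each subgroup.

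The Design section makes the arms differ in contact between participants. Under Treatment condition, "participants in the treatment condition could interact with the other group members by sending text messages", and "The daily walking steps of the participants in this group were displayed to the group", with a daily champion. Under Control condition, participants "did not interact or compare walking steps with other group members".

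The covariate statement under Measures reads "Age, gender, education, race, and self-reported health were used as covariates in the analyses". The Data Analysis Plan compares the arms "using a two condition by three occasions design". It describes the mediation model by condition, change in social engagement and percentage change in steps, and lists no covariates for it. Subgroup appears in none of these places. The documents also give no ICC and do not say whether results refer to the three groups run or to chat groups in general. That each chat group was the ten treated people of one subgroup is the natural reading, but it is not stated.

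**The concern.** Two separate issues arise, and they pull in opposite directions.

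- **Randomisation block.** Balancing the arms within subgroup removes subgroup differences from the treatment contrast. If the model omits subgroup, those differences stay in the error term. The standard error is then too large and precision is lost.
- **Interacting treated groups.** Contact within the group is the intervention, so outcomes of treated people in the same chat group may be correlated while controls stay independent. If the results are to carry over to new chat groups, variation between groups belongs in the standard error, and the planned models leave it out.

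At stake are some lost precision on the first count and, if its conditions are met, overstated certainty on the second.

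**Working it through.** **Inputs.** From the documents: 3 subgroups, 10 treated and 10 control in each, five covariates. The documents give no figure for subgroup variation or ICC, so there is no plan figure to reproduce; the stated sample size does not use either. Every subgroup SD below (in units of the within-subgroup SD of the analysed quantity) and every ICC is an assumption. Type I errors are two-sided against a nominal 5% and, unless marked analytic, come from simulation; repeat runs agree within about 0.2 of a percentage point.

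**Step 1: block omitted, ICC 0.** Subgroup effects cancel in the difference between arms. In the pooled error they add 10 × 2 × SD² to the sum of squares in each arm, 40 × SD² in total on 58 df. The standard error is therefore too large by about √(1 + 40 × SD²/58).

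- SD 0.2 / 0.4 / 0.6: √1.028 / √1.110 / √1.248 = 1.014 / 1.054 / 1.117.
- Type I error: about 4.8 / 4.0 / 3.1%.

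A difference constant over occasions drops out of the condition-by-occasion interaction, which stays at about 5%. It also drops out of simple change scores, such as the mediator. In percentage change it drops out of the numerator, though pretest steps remain in the denominator. For the interaction and simple change scores, adding subgroup gains precision only if subgroups differ in change.

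**Step 2: cost of adding subgroup.** With five one-df covariates, error df go from 60 − 2 − 5 = 53 to 51. The critical t goes from 2.0057 to 2.0076, a ratio of 1.0009.

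**Step 3: inference to the three groups run.** Over ICC 0 to 0.20, type I error is 5.0 to 4.2% as planned with no subgroup difference, 4.0 to 3.4% as planned at SD 0.4, and 5.0 to 4.6% at SD 0.4 with subgroup in the model. None exceeds 5%.

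**Step 4: inference to new groups of ten.** With unit total variance, the true variance of the difference is (1 + 9 × ICC)/30 + 1/30, while the planned model uses 2/30. The ratio is (2 + 9 × ICC)/2, and the analytic type I error is 2 × (1 − Φ(1.96/√ratio)).

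| Assumed ICC | 0 | 0.01 | 0.05 | 0.10 | 0.20 |
|---|---|---|---|---|---|
| Treated-arm multiplier, 1 + 9 × ICC | 1 | 1.09 | 1.45 | 1.90 | 2.80 |
| Variance ratio | 1 | 1.045 | 1.225 | 1.45 | 1.90 |
| Standard error ratio | 1 | 1.022 | 1.107 | 1.204 | 1.378 |
| Analytic type I error, % | 5.0 | 5.5 | 7.7 | 10.4 | 15.5 |
| As planned, no subgroup difference, % | 5.0 | 5.5 | 7.6 | 10 | 16 |
| As planned, SD 0.4, % | 4.0 | 4.5 | 6.2 | 8.8 | 14 |
| Subgroup added, SD 0.4, % | 5.0 | 5.6 | 7.6 | 10.7 | 16.5 |
| Subgroup added and variance inflated, SD 0.4, % | 5.0 | 5.0 | 5.1 | 5.4 | 5.7 |

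The condition-by-occasion interaction with five covariates, no subgroup difference and the ICC defined on change gives about 5.5 / 7.3 / 10 / 16% at ICC 0.01 / 0.05 / 0.10 / 0.20. With both mediator and outcome clustered, the test of the direct effect in the mediation model gives about 7 to 8 / 10 to 11 / 15 to 16% at ICC 0.05 / 0.10 / 0.20.

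The SD 0.4 rows show that the omitted block partly offsets the clustering. Adding subgroup alone removes that offset.

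**The case against.** The strongest reply is that no error in the plan's own inference is shown. The block omission is conservative, and it vanishes in the interaction, which is the test closest to the stated objective, unless subgroups differ in change. The documents give no evidence that they do. The clustering effect needs an intended generalisation, a positive ICC and a particular chat-group composition, none of which is stated. The Objectives section also says "This pilot study explored the efficacy of one function of the app WeChat", and its aims are exploratory.

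Most of this stands, and it sets the weight of the point. It does not remove the case for fitting the factor used in the allocation, which needs no unstated condition and costs almost nothing. Nor does it settle scope, on which the documents are silent. The reported sensitivity analysis does not help: it dropped the covariates and did not touch grouping.

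A reader might infer that the trial's tests are invalid because clustering was ignored, and take the 16% as their true error rate. The documents do not support that. The figure needs an ICC of 0.20 and a new-groups target, and it falls to about 14% if subgroups differ with SD 0.4. A reader might equally infer that a subgroup term cures the clustering. Step 4 shows that it does not.

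**Conclusion.** The point holds in a limited form. What follows from the documents alone is that allocation was balanced within subgroup and that neither model includes subgroup. The consequence is conservative and modest, and in the interaction it is nil unless subgroups differ in change.

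The anti-conservative effect is conditional on generalising to new chat groups, on positive within-group correlation, and on each chat group being the ten treated people of one subgroup. Under those conditions its size runs from negligible at ICC 0.01 to material at 0.10 and above, and the documents cannot place the trial in that range. Severity is minor to moderate.

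**What to change.** 1. Add subgroup (three levels) as an additive fixed factor in the repeated measures ANCOVA, without a condition-by-subgroup term, and as two indicator covariates in both PROCESS equations. Label this post hoc: the protocol records "follow-up data collection completed in March 2019" and already reports a sensitivity result.
2. Because step 1 removes the offsetting conservatism, pair it with one of the following.
   - State that inference is limited to the three groups run.
   - If generalisation is intended, first state the chat-group composition. If each chat group was the ten treated people of one subgroup, report a sensitivity table with the treated-arm variance multiplied by 1 + 9 × ICC at ICC 0, 0.01, 0.05, 0.10 and 0.20. Define the ICC on change for the interaction and for PROCESS. Apply the inflation to the a-path (with a Monte Carlo interval for the indirect effect) and to the total and direct effects. If all 30 treated people shared one chat, the group effect cannot be separated from treatment and the table does not apply.
3. Note that an ICC estimated from three groups is very imprecise, which is why the table uses assumed values.

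**Cost.** Re-analysis of data already held, and two degrees of freedom. The scope statement is one sentence. Intervals in the table widen by about 2 / 11 / 20 / 38% at ICC 0.01 / 0.05 / 0.10 / 0.20. The main risk is doing step 1 without step 2 while presenting results as general: at SD 0.4 and ICC 0.05, type I error would rise from about 6.2 to 7.6%.

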The study was approved by the University's Institutional Review Board. The clinical trial was registered at the US National Institutes of Health (ClinicalTrials.gov). After the participants were deemed eligible to participate in the study, participants were randomly assigned to one of two conditions: treatment or control. During the 4-week study, participants were blinded to condition. Data collection was also blinded to the experimenters, as the survey and physical activity data were collected through online platforms (Qualtrics and WeRun, respectively).

All participants completed a survey with demographic questions and the self-report outcome measures at pretest. They were asked to use WeRun to track their own daily steps for one week, prior to being assigned to groups. This provided pretest physical activity data and helped participants become familiar with WeChat and syncing the data with their phone. After 4 weeks of using the application, all participants completed the same self-report measures to assess changes in the outcomes of interest. They also completed a follow-up assessment 1 month after the post-test for the same measures.

During the intervention, participants' daily walking steps were recorded by WeRun, and the data were logged by the research assistant every day. The research assistant also recorded each participants' daily ranking and number of social interactions in the treatment condition. Messages were sent by email and WeChat messages to the participants to remind them to carry their phone with them as often as possible during the day and use the application every day. The trained research assistant explained how to use WeChat, WeRun to all participants. Participants in both conditions were asked to use the application every day. A message was sent to remind them to use the application if they had not done so for three consecutive days.

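### Percent change from a single pretest week that was also the activity screen drifts upward and enlarges a real treatment effect in percentage points; moving the mediation outcome to the log scale removes the enlargement but not all of the within-arm rise

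*Combined protocol and SAP*

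**What the plan says.** Four statements in the combined protocol and SAP bear on this.

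- **Definition** (Measures, Daily step counts). "Percentage change in mean weekly steps at posttest was calculated as the difference between the mean weekly steps at posttest and pretest divided by" the pretest mean. Follow-up has the same form. Each week's value is "calculated as the mean number of steps across the 7 days in that week of the study".
- **Source of the denominator** (Design). "They were asked to use WeRun to track their own daily steps for one week, prior to being assigned to groups". The same week had a second purpose: "This provided pretest physical activity data and helped participants become familiar with WeChat and syncing the data with their phone".
- **Screen on that week** (Methods, Sample). People counted as physically active ("i.e., who had 7,000 - 10,000 daily steps or above everyday) were not included after the one-week baseline").
- **Use** (Data Analysis Plan). The mediation model tests total, direct and "indirect effects of intervention on percentage of change of mean weekly steps from pre-test to post test". Percent change is the only outcome named for that model. Steps themselves are compared between arms by repeated measures ANCOVA of mean daily steps.

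The listed covariates are age, gender, education, race and self-reported health. Pretest steps are not among them. The plan does not mention variability of the pretest week, regression to the mean or a log scale.

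**The concern.** A ratio with a noisy denominator is biased upward. A chance low pretest week can produce a very large positive value, while a fall can never go below -100%. The screen adds to this: people were kept partly because their pretest week was low, so chance low weeks are over-represented and the posttest week tends to be higher for that reason alone.

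Two readings are at stake. A rise in the control arm could be taken as improvement when part or all of it is artefact. And the total effect of condition, which in this model is a difference in mean percentage points, would be larger than the true proportional effect. The mediation model serves the second stated objective, the mechanism of behaviour change, so its effect sizes will be quoted.

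**Working it through.** **Stated figure.** The documents give no figure for the drift or variability of percent change. The one design figure (56 participants, effect 0.3) is not tied to this parameter and is not used here.

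**Inputs.** From the documents: the definition, one pretest week, the screen on that week, 30 per arm. Assumed, because the documents do not give them: log-normal steps, median 5,000, between-person log SD 0.45, week-to-week log SD s from 0.15 to 0.5, people kept if the pretest mean is below 8,500, and a proportional treatment effect of exp(0.3) = 1.35.

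**Model with no true change.** Y0 = exp(m + e0) and Y1 = exp(m + e1), where e0 and e1 are independent with SD s. Let S² = 0.45² + s², r = 0.45²/S² and k = log(8,500/5,000)/S.

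- Without a screen, mean percent change is exp(s²) - 1 and the mean log ratio is 0.
- With the screen, mean percent change is D = exp(s²) × Φ(k + (1 - r)S)/Φ(k) - 1.
- With the screen, the back-transformed mean log ratio is G = exp[(1 - r)S φ(k)/Φ(k)] - 1.

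**Treatment effect.** The treated mean is 1.35(1 + D) - 1 and the control mean is D. Their difference is 0.35(1 + D). On the log scale D and G cancel between arms, which leaves a ratio of 1.35.

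**Worked case, s = 0.3.** S² = 0.2025 + 0.09 = 0.2925, so S = 0.541, r = 0.692, k = 0.531/0.541 = 0.981 and (1 - r)S = 0.166. Then D = 1.0942 × 0.8744/0.8367 - 1 = 14.3%. The true 35% reads as 35 × 1.143 = 40.0 points. G = exp(0.166 × 0.2465/0.8367) - 1 = 5.0%.

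| s | r | Drift, no screen | Drift D, screened | True 35% reads as | Log ratio rise G |
|---|---|---|---|---|---|
| 0.15 | 0.90 | 2.3% | 3.4% | 36.2 points | 1.2% |
| 0.2 | 0.84 | 4.1% | 6.2% | 37.2 points | 2.1% |
| 0.3 | 0.69 | 9.4% | 14.3% | 40.0 points | 5.0% |
| 0.4 | 0.56 | 17.4% | 26.5% | 44.3 points | 9.3% |
| 0.5 | 0.45 | 28.4% | 43.5% | 50.2 points | 14.8% |

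G is about a third of D throughout (for example 5.0/14.3 = 0.35).

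**Type I error and power.** In simulated trials of 30 per arm with no treatment effect, type I error was about 0.05 on both scales. Power for a true 35% effect at s = 0.2 / 0.3 / 0.4 / 0.5 (repeat runs agree to within about two points):

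- percent change: 98 / 75 / 50 / 34%
- log ratio: 98 / 78 / 56 / 40%
- log posttest with log pretest as covariate: 99 / 82 / 62 / 47%

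**Sensitivity to the screen.** The wording does not settle whether the limit is 7,000 or 10,000, or whether it applies to the week's mean or to every day. The recruitment counts do not settle it either. 241 - 38 - 143 = 60 holds only if the 15 + 4 + 4 + 3 = 26 listed cases lie inside the 38. That leaves 38 - 26 = 12, who may be the active exclusions (12 of 72, one sixth), but this is inference. With s from 0.15 to 0.35, between-person log SD 0.35 or 0.50 and a true 20% effect:

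- no screen: 20.4 to 22.6 points
- cut-off of 7,000 on the week mean: up to 24.8 points (a factor of 1.24)
- log ratio: 20.0% in every setting
- spurious rise in the log ratio: +1.3% to +7.8% with the top sixth removed, +1.9% to +11.1% with the 7,000 cut-off, and about +1% to +2% if the screen means 7,000 or more on all seven days

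**The case against.** The case for leaving the plan alone has real weight.

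- **The arm comparison is not falsely positive.** The pretest week and the screen come before assignment, so the drift is the same in both arms in expectation. With no treatment effect the expected difference is zero. This stands. A reader might infer that percent change manufactures a treatment effect, and nothing in the documents supports that.
- **The main step comparison is separate.** It is a repeated measures ANCOVA of mean daily steps and does not use percent change. This stands.
- **The log ratio is not a full cure.** A reader might infer that it shows no rise when nobody changed. That would hold without the screen, but the screened week is still the baseline, so regression to the mean remains. Any under-recording while people learned the app would also remain, although the documents do not show that it occurred.
- **The inflation comes from subtracting percentages.** The between-arm ratio of (1 + mean percent change) returns 1.35 in expectation. This is true, but the mediation model estimates differences in the outcome and not that ratio.
- **The larger figures need a noisy week.** A log SD of 0.4 or 0.5 implies week-to-week correlations of 0.56 or 0.45 before screening, which nothing in the documents supports. At 0.2 the log ratio gains no power and the inflation is about 2 points.
- **The indirect effect was not simulated.** The calculations concern the effect of condition on the outcome. How the inflation divides between direct and indirect effects, and whether a few people with low pretest counts dominate the fit, has not been shown and is not claimed.

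**Conclusion.** The concern holds in limited form. As defined, percent change rises on average when nobody changes, and it multiplies a real proportional effect, read in percentage points, by (1 + drift). That direction follows from the definition under any multiplicative week-to-week noise; the size does not. It rests on an assumed week-to-week SD, an assumed reading of the screen and a proportional effect. Over the range examined the multiplier runs from about 1.02 (stable week, no screen) to 1.43 (log SD 0.5, cut-off 8,500).

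The fault is one of effect size and interpretation in the mediation analysis, and it does not affect the validity of the test of condition. In the settings examined the log scale removed the between-arm inflation and had power that was equal or better. It does not make within-arm change interpretable. This is a worthwhile, inexpensive correction and not a threat to the trial's main step comparison.

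**What to change.** In Measures (Daily step counts) and the Data Analysis Plan:

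1. Make log mean daily steps at posttest the mediation outcome, with log mean daily steps at pretest as a covariate. At minimum, use the log ratio of the two weeks. Define follow-up in the same way.
2. Report the back-transformed between-arm ratio as the effect. Keep arithmetic percent change as a descriptive figure only.
3. State that within-arm rises are not read as improvement, because the pretest week was also the screen.
4. Clarify how the activity screen was applied (which limit, and to the week's mean or to each day), since this sets the size of the regression to the mean.

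The cost is a change of wording, one data step in SPSS and one added covariate, with no new data. The effect becomes a ratio of geometric means, which needs a sentence of explanation. A week with a recorded mean of zero cannot be logged, so a rule for it is needed; percent change likewise fails when the pretest week is zero.

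### The step test is described as covering the intervention period but uses only the pretest, post-test and follow-up weeks, treats pretest as an outcome, and puts participants with one missing occasion at risk of exclusion

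*Combined protocol and SAP*

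**What the plan says.** The Data Analysis Plan uses repeated measures ANCOVA "to test for effects of the treatment on mean daily step counts over the intervention period", and in the same sentence compares the arms "at pretest, posttest, and follow-up using a two condition by three occasions design".

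The Design section says of the intervention steps that "the data were logged by the research assistant every day". The Measures section (Daily step counts) says that steps were recorded "by the end of each day during the 4-week intervention period and at the 1 month follow up". For analysis, however, it defines only these variables: "Mean daily steps for pretest week, post-test week and one month follow up week". The mediation outcome, percentage change in weekly steps, also runs from pretest to post-test.

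The Objectives section asks whether the treatment arm shows "greater increases and higher maintenance of daily steps". The covariates listed are age, gender, education, race and self-reported health; pretest steps are not among them. No rule is given for missing days or missing occasions, no analysis population is defined, and no dropout count or allowance is stated.

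**The concern.** There are three linked problems.

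- **Target.** The text names the intervention period, but the model sees one week of it. A reader cannot tell whether the step result is a four-week average or an end-of-intervention level.
- **Precision.** With pretest as one of three outcome occasions, the pretest-to-posttest treatment effect is a difference between arms in mean change. Using pretest as a covariate is more precise, which matters with 30 per arm.
- **Missing occasions.** Standard repeated measures ANCOVA works on participants with every occasion present. Someone without a follow-up week would also leave the posttest comparison. If less engaged people were the ones missing, the posttest result could be biased as well as less precise.

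**Working it through.** **1. Which weeks are used.** The Design and Measures sections together describe six recorded weeks: one pretest, four intervention and one follow-up. The defined means cover three. That the post-test week is intervention week 4 is implied rather than stated, but it is the natural candidate: the posttest falls at the end of week 4, and no other recording between then and the one-month follow-up is described. Unused: 6 - 3 = 3 weeks, namely intervention weeks 1-3.

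**2. The plan's own sample size.** Methods (Eligibility) gives 56 for more than 80% power at a correlation of 0.3 and p < .05. Read literally as a test of a correlation, this needs 82-85 participants two-sided or 64-68 one-sided. The G*Power test family is not stated and some settings do land at 55 or 56, so 56 is not shown to be wrong. Nothing below depends on it except the margin in step 5.

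**3. Variance per participant.** The documents give no SD and no week-to-week correlation. Assume unit variance in every week and one common correlation r between weeks.

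- Change score, week 4: 2(1 - r)
- Baseline-adjusted, week 4: 1 - r²; ratio to the change score (1 - r²)/[2(1 - r)] = (1 + r)/2
- Baseline-adjusted, mean of weeks 1-4: (1 + 3r)/4 - r²

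| r | Change score, week 4 | Adjusted, week 4 | Ratio | Adjusted, four-week mean | Ratio to adjusted week 4 |
|---|---|---|---|---|---|
| 0.6 | 0.80 | 0.64 | 0.80 | 0.340 | 0.531 |
| 0.7 | 0.60 | 0.51 | 0.85 | 0.285 | 0.559 |
| 0.8 | 0.40 | 0.36 | 0.90 | 0.210 | 0.583 |

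Baseline adjustment alone cuts the week-4 variance by 20%, 15% and 10%. Moving from week 4 to the four-week mean cuts it by a further 46.9%, 44.1% and 41.7%. In standard errors, the four-week mean is at 0.73-0.76 of adjusted week 4 (square roots of the last column). With correlations that decay over time (AR(1)) the ratio is 0.70-0.72, so the pattern does not hang on the common-correlation assumption.

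**4. Does the four-week mean have more power?** Take 30 per arm, two-sided 5%, and an assumed effect of 0.5 SD in week 4. If the effect builds linearly, the average effect is (0.25 + 0.50 + 0.75 + 1)/4 = 0.625 of the week-4 effect, or 0.3125 SD.

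| r | Week 4, adjusted | Four-week mean, constant effect | Four-week mean, linear build-up |
|---|---|---|---|
| 0.6 | 68% | 91% | 55% |
| 0.7 | 77% | 95% | 62% |
| 0.8 | 90% | 99% | 75% |

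The four-week mean has more power only when its effect exceeds about 0.73-0.76 of the week-4 effect. A linear build-up, at 0.625, falls short.

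**5. Missing occasions.** The margin over the stated requirement is 60 - 56 = 4 participants (4/60 = 6.7%), so five incomplete participants would use it up. The missing rates here are assumptions. With 5% missing at posttest and 5% at follow-up, complete cases number 60 x 0.95² = 54 if independent and 60 x 0.95 = 57 if the same people miss both. With 10% at each, they number 60 x 0.90² = 49 if independent and 54 if overlapping. The standard error rises by a factor of 1/√0.9 = 1.05 at 54 participants and 1/0.9 = 1.11 at 49.

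**The case against.** The strongest reply is that one loose phrase is being set against a plan that is otherwise consistent. The Measures section defines the three weekly means, the analysis sentence names the three occasions, the mediation outcome is pretest to post-test, and the objective of increase and maintenance is served by an end-of-intervention week and a follow-up week. This stands in large part. It is why week 4 should remain the main comparison and why the phrase should be corrected, rather than the four-week average promoted to primary.

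It also stands that the large gain belongs to a different question. With complete data and a full condition-by-week model, weeks 1-3 add essentially nothing to the week-4 contrast; the gain there comes from baseline adjustment. And a mixed model does not guarantee all 60: a person with no pretest steps, a missing covariate or no later week at all would still be left out. The pretest gap is unlikely, since inactivity in the baseline week was part of selection.

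Three stronger readings are tempting and are not supported:

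- A reader might infer that randomised participants were lost. No deletion rule and no missing count is given, and the Sample section speaks of the 60 as having completed the study in three subgroups. The reminders to people who stopped using the app show that gaps were foreseen, not that occasions were missing.
- A reader might infer that most step data are discarded. It is three weeks of six.
- A reader might infer that averaging four weeks must raise power. It can lower it, as step 4 of the working shows.

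The reply does not answer the fact that the stated target and the computed quantity differ, that pretest is handled less efficiently than it could be, and that nothing says what happens to a participant with one occasion missing.

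**Conclusion.** The point holds as a limited one that should be corrected. That the wording and the analysed weeks disagree, and that intervention weeks 1-3 go unused, follows from the text alone. The efficiency loss from using pretest as an occasion is 10-20% of the variance of the week-4 contrast, for assumed correlations of 0.8 down to 0.6 and equal variances. The further 42-47% available from the four-week average requires a constant effect from week 1 and answers a different question. Exclusion of incomplete participants is a property of the usual method combined with a missing rule that the plan does not give; its size here is unknown and may be zero. None of this shows that the trial's step result is invalid.

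**What to change.** - Analyse steps with a linear mixed model on weekly means for weeks 1-4 and the follow-up week. Include pretest-week steps as a baseline covariate, condition, week, condition by week, the three subgroups and the stated covariates, and use all available data.
- Keep the week-4 (posttest) contrast as the main comparison, consistent with the Measures section and the mediation outcome. Report the weeks 1-4 average as a secondary contrast and the follow-up contrast for maintenance.
- Reword the Data Analysis Plan so that the description of the step test matches, and state that the post-test week is week 4 if that is so.
- Use the same model form for the two questionnaires at posttest and follow-up, with the pretest score as covariate.
- State rules for missing days within a week and for missing occasions, and report the number observed per arm at each occasion.

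The cost is SAP wording and a change of procedure within SPSS on data already held, one extra reported contrast, and reliance on a missing-at-random assumption. Because the plan is written in the past tense and already reports a sensitivity result, a re-analysis in this form should be labelled as such.
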